5.8.3 Serious Adverse Events

All serious adverse events occurring during the 180-days of study participation will be recorded. Adverse events and serious adverse events are critical endpoints and will be assessed as they occur and at the scheduled clinic visits. A serious adverse event is one that is fatal or life-threatening, is permanently or substantially disabling, requires or prolongs hospitalization, or any event that the treating clinician judges to be a significant hazard, contraindication, side effect, or precaution. For each recorded serious adverse event, the patient's attending physician will be asked to classify the causal relationship of the event to the study treatment as probable, possible, unlikely, and unrelated. Detailed form and narrative reports of the following specific adverse events will be obtained:

- Death (all cause) within 30 days of enrollment
- Death within 7 days of enrollment: Immediate peri-procedural death
- Symptomatic Re-Hemorrhage or New Hemorrhagic Event: any new intracranial hemorrhage or increase in size of pre-existing hemorrhage (IPH, IVH or extra-axial bleed) within 30 days associated with an increase of 4 or more points on the NIHSS or GCS increase ≥2 persisting for at least 24 hours and/or requiring emergency surgical decompression or resulting in death^{5, 6}.
- Symptomatic Evolution of Peri-hematomal Edema: Edema with increased mass effect or uncontrolled ICPs within 30 days requiring emergency surgical decompression NOT related to new or increased hemorrhage (i.e. edema related) associated with an increase of 4 or more points on the NIHSS or GCS increase ≥2 persisting for at least 24 hours, requiring emergency surgical decompression or resulting in death.
- Symptomatic Ischemic Stroke: A new ischemic stroke (ipsilateral, contralateral; contiguous with bleed/operative site or remote; cortical, subcortical or perforator distribution) within 30 days associated with an increase of 4 or more points on the NIHSS or GCS increase \geq 2 persisting for at least 24 hours, requiring emergency surgical decompression or resulting in death.
- Surgical complications related to Apollo /Artemis MIES: Surgical site infection, brain abscess or confirmed meningitis, or documented complication(s) deemed specifically related to the procedural anesthetic (medication, access or intubation related) within 30 days.

A medical monitor will review these specific categories of events. The DSMB will also function as the CEC and will review all events at regularly scheduled DSMB meetings, which will occur at approximately 6-month intervals during the study. The medical monitor has the authority to alert the DSMB at any time if a potential safety issue arises. If at any point, these reviews raise any safety concerns, the DSMB will be empowered to suggest that the trial be placed on hold and request additional analyses of the trial dataset. The DSMB will issue reports for each meeting. The DSMB will be composed of three cerebrovascular specialists and a statistician. Safety stopping rules for the primary safety endpoint will be developed and used to help the DSMB make its safety assessments. These stopping rules will be explicitly stated within the DSMB charter.

6. Study Primary Endpoints

Primary Endpoint:

The primary objective of this multicenter prospective registry is to provide an additional safety, technical and clinical outcomes data for minimally invasive endoscopic surgery (MIES) with Apollo /Artemis for the evacuation of brain hemorrhage in patients who do not qualify for the concurrent INVEST Feasibility study at active INVEST centers:

- Clinical Efficacy Endpoint: 180-day global disability assessed via the modified Rankin score (mRS), categorized as either mRS  3
- Technical Efficacy Endpoint: Rate of surgical success
 - Predominantly or Only ICH: Reduction to < 15 cc total volume AND >60% reduction in hemorrhage volume on immediate post-treatment CT scan.⁴
 - Predominantly or Only IVH: mGraeb score of ≤ 5 on day 7 CT scan⁷
- Safety Endpoint: Rate of mortality at 30 days

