The INVEST Feasibility study was specifically designed to provide an assessment of enrollment and follow up for this patient population after being treated with Apollo / Artemis MIES. There are other patients who will come to the INVEST centers who, in the experienced physicians' opinion, may benefit from the Apollo / Artemis MIES procedure, but are excluded from the feasibility study protocol for various reasons (e.g., large IVH with a small ICH, low admitting GCS score, large hemorrhage (>80cc), baseline mRS >1). In some cases, physicians at INVEST centers may decide to offer Apollo / Artemis MIES to these patients outside of the INVEST Feasibility study. The INVEST registry will allow experienced operators at these INVEST centers to enroll such patients into a prospective observational registry. This mechanism serves several important purposes. First, the INVEST REGISTRY data may be informative to a subsequent pivotal Phase III trial in conjunction with the concurrent INVEST feasibility study. Second, these data will provide a valuable surveillance of the application of MIES surgery and the Apollo system / Artemis Device in clinical practice at major academic institutions within the controlled, monitored setting provided by an observational registry. A core lab will assess technical outcomes in these patients independently. The study's Medical Monitor and Data Safety Monitoring Board (DSMB) will actively monitor clinical outcomes. Finally, the registry allows centers to enroll most all patients who are considered candidates for Apollo / Artemis MIES into a prospective study. It is our opinion that such a mechanism will facilitate the Feasibility enrollment at INVEST centers and will enhance the efficiency of the study. Avid enrollment in the INVEST studies increases protocol awareness, familiarity with mechanisms for screening and enrollment, familiarity with both protocols and protocol adherence.

The INVEST REGISTRY will allow the inclusion of patients with low presenting GCS (≤ 4). Patients with very low presenting GCS (3-4) represent a heterogeneous group. Many will have severe unrecoverable injuries potentially involving the brain stem. We did not want to potentially dilute our ability to detect a signal for a treatment effect by

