5.1 Imaging Assessment for Eligibility for Trial Participation

The subject should be clinically evaluated in the same manner as any patient with non-traumatic spontaneous intraparenchymal hemorrhage. Clinical assessment documenting NIHSS, GCS, baseline mRS and significant past medical history should be obtained. Imaging with CT and CTA (MRA is acceptable in CTA ineligible patients) is required to confirm the diagnosis of ICH and exclude a vascular etiology. Cerebral hemorrhage volume will be measured using an A x B x C/2 algorithm. IVH will be quantified using a mGraeb score. Additional anatomic, vascular and physiologic imaging with MRI, MRA or conventional angiography per the institutional standard of care should then be performed on patients as part of a standard evaluation for non-spontaneous hemorrhage etiology. In patients with a CTA "spot sign" on presentation imaging, a follow up CTA must be performed at 12 hours to verify resolution of this finding prior to enrollment. Increase in cerebral hematoma size of ≤ 5 cc will be considered "stable" on the stability scan. In the case that the stability scan demonstrates hemorrhage volume increase > 5 cc, a second stability scan can be obtained q12 hours until either stability is demonstrated or the patient is outside of the window for treatment (72 hours from the time of ictus). Ventricular hemorrhage will be considered stable if the mGraeb score increases by ≤ 3 points on the stability scan. Similarly, if the mGraeb score increases more than 3, a follow up scan can be performed in 12 hours to establish stability. Patients meeting all inclusion and no exclusion criteria will be eligible for enrollment after an acceptable stability scan.

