5.8 Follow-Up Examination

5.8.1 Clinical

Several clinical outcome measures were selected for this study. These were chosen on the basis of their reliability, familiarity to the neurologic community, adaptability for use in patients who have had a stroke, and comparability to end points used in other trials of intracranial hemorrhage. All scores will be recorded in source documentation and entered into the electronic case report forms.

- 1. modified Rankin Scale (mRS, Appendix 4): mRS is an overall assessment of global handicap. In the original Rankin Scale, a score of zero indicates the absence of symptoms and a score of 5, severe disability. The modified Rankin Scale adds a score of 6 for fatal outcomes. A historical mRS will be obtained to assess the patient's level of function prior to the ICH. The score will be repeated as specified in Table 1.
- 2. The National Institutes of Health Stroke Scale (NIHSS, Appendix 5) is a 42-point scale that quantifies neurologic deficits in 11 categories. Normal function without neurologic deficit is given a score of zero. NIHSS should be done by a certified examiner as close to the specified times as possible.
- 3. EQ-5D-5L (Appendix 6) is a standardized instrument for use as a measure of health outcome. Applicable to a wide range of health conditions and treatments, the questionnaire provides a simple descriptive profile and a single index value for health status.

All day 7, discharge, day 30, day 90 and day 180 clinical outcome measures will be assessed by a qualified member of the research or clinical team either in person at a clinic visit, by phone or by mailed questionnaire. The schedule of neurological assessments is listed in Table 1. At each visit, the patient's medical record will be surveyed for any new or interim neurological adverse or serious adverse events. In addition, the patient or LAR will be asked about any interim neurological adverse or serious adverse events. The subject or LAR will also be specifically asked about any interim neurosurgical procedures.

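### The GCS limb of the symptomatic re-hemorrhage and ischemic stroke definitions cannot register worsening from a reference GCS of 3-4, a group the registry deliberately admits

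*Combined protocol and SAP*

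**What the plan says.** Section 5.8.3 lists specific adverse events that receive detailed forms and narratives. Section 7.5.2.1 repeats them as the endpoints that the medical monitor assesses and presents.

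- **Re-hemorrhage and ischemic stroke** within 30 days qualify through "an increase of 4 or more points on the NIHSS or GCS increase ≥2 persisting for at least 24 hours". Emergency decompression and death are further routes. For re-hemorrhage, 5.8.3 writes "and/or requiring emergency surgical decompression or resulting in death". For stroke it uses a comma list, "persisting for at least 24 hours, requiring emergency surgical decompression or resulting in death", which 7.5.2.1 turns into and/or.
- **Edema** opens differently: "Edema with increased mass effect or uncontrolled ICPs within 30 days requiring emergency surgical decompression NOT related to new or increased hemorrhage". Decompression is thus already in the definition at any baseline score.

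The rationale section (under section 2) states: "The INVEST REGISTRY will allow the inclusion of patients with low presenting GCS (≤ 4". It then equates this group with scores of 3 to 4: "Patients with very low presenting GCS (3-4) represent a heterogeneous group". Section 5.8.1 says the NIHSS "is a 42-point scale that quantifies neurologic deficits in 11 categories", with zero as normal.

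No provision is made for a patient already at the bottom of the GCS. Neither section names the assessment from which the score change is measured, although Table 1 schedules GCS and NIHSS at baseline, stability, post-procedure, discharge or day 7, and each later visit.

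**The concern.** A threshold defined as a change in score works only if the patient has room to change. The documents treat 3 as the lowest GCS, so a patient whose reference score is 3 or 4 cannot fall by 2 points. The wording asks for a GCS *increase*, although the rationale treats a low GCS as the severe end. Read literally, the limb counts improvement. Read as a decline, it is out of reach from 3-4. Neither reading lets it register worsening in these patients, so correcting the direction alone would leave the gap.

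What is at stake is the comparability of the named-event rates. The rationale says data on GCS 3-4 patients may inform the pivotal trial by setting their outcomes beside those of GCS 5-8 patients in the feasibility study. For re-hemorrhage and stroke, the ability to detect a non-fatal event changes at exactly that boundary, in the direction of fewer counted events in the sicker group. The same categories go to the medical monitor and DSMB, and section 6.1 analyzes the specified adverse events in the as-treated sample.

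**Working it through.** The plan gives no figure of its own on this point. The check is range arithmetic followed by an illustration of size.

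**Inputs from the documents.** Required change: NIHSS up by at least 4, or GCS by at least 2, for 24 hours (5.8.3). Lowest GCS: 3 (rationale). NIHSS maximum: 42 (5.8.1). Re-bleeding: 2/29 = 6.9% (2.1). Enrollment: up to 50 (4.5).

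**Assumed.** The number of GCS 3-4 patients and their NIHSS are not given.

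**GCS limb, read as a decline.** Room = reference score − 3.

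| Reference GCS | Room to fall | 2 points possible? |
|---|---|---|
| 3 | 3 − 3 = 0 | no |
| 4 | 4 − 3 = 1 | no |
| 5 | 5 − 3 = 2 | yes |

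GCS 5 is the lowest reference score from which the limb can be met.

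**NIHSS limb.** Room = 42 − reference score.

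| Reference NIHSS | Room to rise | 4 points possible? |
|---|---|---|
| 30 | 12 | yes |
| 36 | 6 | yes |
| 38 | 4 | yes |
| 39 | 3 | no |
| 40 | 2 | no |
| 42 | 0 | no |

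This limb closes only at 39-42.

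**Routes left from a reference GCS of 3-4** (re-hemorrhage and stroke):

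- Reference NIHSS 38 or below: NIHSS rise, decompression or death.
- Reference NIHSS 39 or above: decompression or death only.

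**Illustrative size for re-hemorrhage.** Expected re-bleeds in the subgroup = n × 2/29. The largest understatement of the overall rate is that number divided by 50.

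- n = 10: 10 × 2/29 = 0.69; 0.69/50 = 1.4 points, so 6.9% would read 5.5%. The chance of at least one such re-bleed is 1 − (27/29)^10 = 0.51.
- n = 20: 20 × 2/29 = 1.38; 1.38/50 = 2.8 points, so 6.9% would read 4.1%. The chance of at least one is 1 − (27/29)^20 = 0.76.
- Wider range, n = 5 to 25: 0.34 to 1.72 expected, and the overall rate would read 6.2% to 3.4%.

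These are upper bounds because they require every subgroup re-bleed to be missed. If half were missed, the overall rate would read 6.2% (n = 10) or 5.5% (n = 20).

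**The case against.** A reader might infer that these events cannot be counted in GCS 3-4 patients at all. The documents do not support that, for several reasons.

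- **A score change is not the only route.** Emergency decompression qualifies and is non-fatal. The edema event already requires it in its opening clause, so the floor hardly touches that event. This stands and limits the point to re-hemorrhage and ischemic stroke.
- **The NIHSS may have ample room.** It is an alternative limb, no baseline NIHSS is given for these patients, and the protocol calls them heterogeneous. This stands: exhaustion of both scales is possible but not shown.
- **The reference score is unstated.** A patient who presents at 3-4 and improves after surgery may regain room if change is measured from a postoperative score. This stands too, and is a reason to name the reference.
- **General capture exists.** All SAEs to 180 days are recorded without a score threshold, including any event the clinician judges a significant hazard. The DSMB receives all AEs and SAEs, and all adverse events are tabulated (5.8.3, 7.5.1, 7.5.2.1). The primary safety endpoint is 30-day death. So the named category may be lost, not necessarily the event.

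General capture is only a partial answer. Detailed narratives and the as-treated analysis attach to the named categories. Sections 16 and 16.2 stop recording non-serious events at day 7 or discharge, whichever is earlier, while the named events run to 30 days. A later event not judged serious could go unrecorded.

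The size estimate is also weak. The 2/29 comes from a retrospective series and is cited next to bleeding met during evacuation. It is not shown to be a rate of symptomatic 30-day re-hemorrhage.

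**Conclusion.** The point holds in a limited form. From a reference GCS of 3-4, the GCS limb cannot register worsening: 0 or 1 point of room against 2 required. That is certain from the documents. A non-fatal, non-decompressed re-hemorrhage or ischemic stroke in these patients then depends on a 4-point NIHSS rise, which is impossible from 39-42. How many patients are in that position cannot be determined.

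The consequence is a tendency for the named-category rates to be too low in this subgroup and not comparable with those at GCS 5 or above. For the whole cohort the effect on re-hemorrhage is at most 1.4-2.8 percentage points. That assumes 10-20 of 50 patients at GCS 3-4, the 2/29 rate, and every subgroup event missed. Thirty-day mortality is unaffected, and so is any stopping rule for it. It would go too far to conclude that non-fatal events in the sickest patients disappear from the registry's safety data.

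**What to change.** Keep the symptomatic definitions and make four changes.

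1. Reconcile the direction of the GCS criterion in 5.8.3 and 7.5.2.1, and state which assessment is the reference for the NIHSS and GCS change.
2. Add a core-lab, imaging-defined re-hemorrhage count with no NIHSS or GCS condition. Compare the scheduled post-procedure and day-7 scans with the immediate post-treatment scan. Use the protocol's own stability thresholds: hematoma growth above 5 cc (section 5.1: "Increase in cerebral hematoma size of ≤ 5 cc will be considered" stable), or an mGraeb rise. Section 4.6 treats a rise of 3 or more as unstable and section 5.1 only a rise above 3, so these must be reconciled first.
3. Report this count beside the symptomatic one to the DSMB and in the final tables, split by presenting GCS 3-4 versus 5 or above.
4. Flag patients with reference GCS 4 or below and NIHSS 39 or above as not evaluable on the score criterion.

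Parallel imaging counts for edema and new infarct are not proposed. The plan has no threshold for edema growth, and new infarct is not among the core-lab measures listed in 5.8.2.

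The cost is protocol and DSMB-charter wording plus one table. No visit or scan is added, since 5.8.2 already has the core lab measure hemorrhage volume and mGraeb. There are two downsides: the count will include clinically silent bleeds, and it covers only the scheduled scans, to about day 7, while the symptomatic events run to day 30.

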including these patients in the Feasibility study. However, if operators feel that some patients in this group could potentially benefit from the Apollo / Artemis procedure and intend to treat the patients outside of the INVEST Feasibility, the INVEST REGISTRY will allow the prospective collection of data within the context of a controlled, monitored clinical study. These data may be informative to the subsequent Phase III pivotal trial in that they may indicate a potential for these patients to respond to treatment (i.e., if these registry patients have outcomes similar to GCS 5-8 patients in the feasibility study) or confirm that they do not respond.

The INVEST REGISTRY will include patients with isolated intraventricular hemorrhage (IVH) or IVH with a small ICH. The Apollo system and Artemis Device are cleared for the minimally invasive removal of tissue and fluid from the ventricular system. The INVEST Feasibility is specifically designed for the assessment of this technology to improve outcomes in ICH. The INVEST REGISTRY represents the first prospective study, which will monitor technical and clinical outcomes in patients with IVH.

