7.5.2 Interim Safety Monitoring

7.5.2.1 Stopping the Trial Based on Interim Safety Data

The EOC and DSMB will receive periodic safety reports of all AEs and SAEs. In addition, the following specific endpoints will be assessed by the medical monitor and presented:

- Death (all cause) within 30 days of enrollment
- Death within 7 days of enrollment: Immediate peri-procedural death
- Symptomatic Re-Hemorrhage or New Hemorrhagic Event: any new intracranial hemorrhage or increase in size of pre-existing hemorrhage (IPH, IVH or extra-axial bleed) within 30 days associated with an increase of 4 or more points on the NIHSS or GCS increase ≥ 2 persisting for at least 24 hours, and/or requiring emergency surgical decompression or resulting in death.
- Symptomatic Evolution of Peri-hematomal Edema: Edema with increased mass effect or uncontrolled ICPs within 30 days requiring emergency surgical decompression NOT related to new or increased hemorrhage (i.e. edema related) associated with an increase of 4 or more pointon the NIHSS or GCS increase >2 persisting for at least 24 hours and/or requiring emergency surgical decompression or resulting in death.
- Symptomatic Ischemic Stroke: A new ischemic stroke (ipsilateral, contralateral; contiguous with bleed/operative site or remote; cortical, subcortical or perforator distribution) within 30 days associated with an increase of 4 or more points on the NIHSS or GCS increase ≥2 persisting for at least 24 hours and/or requiring emergency surgical decompression or resulting in death.
- Surgical complications related to Apollo / Artemis MIES: Surgical site infection, brain abscess or confirmed meningitis, or documented complication(s) deemed specifically related to the procedural anesthetic (medication, access or intubation related) within 30 days.

Additional details of the monitoring plan will be included in the study SOP and DSMB charter.

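### Three specified adverse event definitions count a GCS increase, not a decrease, as the sign of neurological worsening

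*Combined protocol and SAP*

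**What the plan says.** Section 5.8.3 lists specific events that need fuller documentation: "Detailed form and narrative reports of the following specific adverse events will be obtained". Three of them (symptomatic re-haemorrhage or new haemorrhage, symptomatic evolution of peri-haematomal oedema, and symptomatic ischaemic stroke) carry the same neurological criterion: "increase of 4 or more points on the NIHSS or GCS increase ≥2 persisting for at least 24 hours".

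Section 7.5.2.1 repeats the three definitions for the interim safety reports. Re-haemorrhage there reads "GCS increase ≥ 2 persisting for at least 24 hours, and/or requiring emergency surgical decompression or resulting in death", and ischaemic stroke has the same GCS criterion and connector. The oedema bullet reads "GCS increase >2 persisting for at least 24 hours and/or requiring emergency surgical decompression or resulting in death".

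The link to decompression and death is not uniform. In section 5.8.3 the re-haemorrhage bullet uses *and/or*, but the oedema and stroke bullets use a comma: "persisting for at least 24 hours, requiring emergency surgical decompression or resulting in death". In section 7.5.2.1 all three use *and/or*. Both oedema bullets also require emergency decompression earlier in the sentence, before the neurological criterion.

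On scale direction, section 5.8.1 says that zero on the NIHSS means no deficit. For the GCS, the registry rationale in section 2 says "Patients with very low presenting GCS (3-4) represent a heterogeneous group" and adds "Many will have severe unrecoverable injuries potentially involving the brain stem". It would take it as a sign of potential response "if these registry patients have outcomes similar to GCS 5-8 patients in the feasibility study".

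**The concern.** The criterion joins two changes by *or*, and the two point in opposite clinical directions. An NIHSS rise of 4 is deterioration. A GCS rise of 2, on the protocol's own use of the scale, is recovery. No part of the document states a GCS decrease.

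These are working definitions. They decide which events receive detailed narratives, are reviewed by the medical monitor (section 5.8.3), appear in the periodic reports to the EOC and DSMB (section 7.5.2.1), and are analysed as specified adverse events in the as-treated sample (section 6.1). Applied as printed, they leave out some patients who worsened and admit some who improved while having a new or enlarged lesion. The reported counts could therefore be wrong in both directions. A case report form or programmed check that copies the text would carry the error forward.

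**Working it through.** The plan gives no figure to reproduce, so the check is of wording and logic.

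**Direction of each scale**

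- NIHSS: zero is normal (section 5.8.1), so an increase is worsening.
- GCS: 3-4 is very low, with many unrecoverable injuries, and 5-8 is the better comparison group (section 2, registry rationale). An increase is improvement.

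**Enumeration**

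Assume a qualifying lesion is present. Let N = NIHSS rise of 4 or more (yes/no); GCS = sustained fall of 2 or more, change within 1, or sustained rise of 2 or more; D = emergency decompression (yes/no); X = death (yes/no). That gives 2 × 3 × 2 × 2 = 24 combinations. G is the GCS criterion: a rise as written, a fall as corrected. For each rule, count the combinations whose classification changes when G is corrected.

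*Clauses as alternatives*

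- Re-haemorrhage and stroke, N or G or D or X: G decides only when N, D and X are all no. The fall is missed and the rise is counted, so 2 of 24 change.
- Oedema, D and (N or G or D or X): this reduces to D, so 0 of 24 change.

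*Section 5.8.3 comma read as adding a condition*

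- Stroke, (N or G) and (D or X): N is no, GCS is a fall or a rise (2), and D or X is present (3 ways). 2 × 3 = 6 of 24 change.
- Oedema, D and (N or G): N is no, GCS is a fall or a rise (2), D is yes, X is either (2). 2 × 2 = 4 of 24 change.

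| Definition | Section | GCS wording | Link | Combinations changed |
|---|---|---|---|---|
| Re-haemorrhage | 5.8.3 | increase ≥2 | and/or | 2 |
| Oedema | 5.8.3 | increase ≥2 | comma | 0 or 4 |
| Stroke | 5.8.3 | increase ≥2 | comma | 2 or 6 |
| Re-haemorrhage | 7.5.2.1 | increase ≥2 | and/or | 2 |
| Oedema | 7.5.2.1 | increase >2 | and/or | 0 |
| Stroke | 7.5.2.1 | increase ≥2 | and/or | 2 |

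**What remains after the direction is corrected**

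If the comma is cumulative, the two sections still disagree.

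- Stroke: the alternatives rule is met in 24 − 2 = 22 combinations. The cumulative rule is met in 4 × 3 = 12 (four N-by-GCS pairs satisfy N or G; three D-by-X pairs satisfy D or X). Difference: 10 of 24.
- Oedema: D alone holds in 12; D and (N or G) holds in 4 × 2 = 8. Difference: 4 of 24.

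**Oedema threshold**

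Split a fall of exactly 2 from a fall of 3 or more, giving 2 × 4 × 2 × 2 = 32 combinations. With the direction corrected, ≥2 and >2 differ in 0 of 32 as alternatives and 2 of 32 as cumulative.

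**Scale, for re-bleeding only**

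Section 2.1 reports re-bleeding in 2 of 29 earlier patients (6.9%; exact 95% interval 0.8% to 22.8%). Assuming that rate applies to the 50-patient ceiling in the synopsis and section 4.5, 50 × 2/29 = 3.4 events, range 0.4 to 11.4. Section 2.1 does not say that those re-bleeds were symptomatic, and only events decided solely by the GCS criterion would be misclassified. This is context for how small the counts may be, not an estimate of patients affected.

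**The case against.** The best defence is that the intent is obvious. Each event is headed as symptomatic, the change must be associated with the lesion, and the re-haemorrhage bullet in section 5.8.3 cites two papers whose titles concern neurological deterioration. The DSMB, which also acts as the CEC, has three cerebrovascular specialists and reviews all events; they may well read past the slip. That is plausible, but it means the definition applied would differ from the one written, and it does not protect text copied into forms or programs.

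The consequences are also contained. The stopping rules announced in section 5.8.3 concern the primary safety endpoint, which is 30-day mortality. The statistics are descriptive, serious events are recorded to 180 days whatever their category, and NIHSS and GCS are collected at scheduled visits, so many events could be reclassified later. All of this stands and limits the severity.

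The cumulative reading of the comma is strained. It would mean that a new stroke with a sustained 4-point NIHSS rise is not symptomatic unless decompression or death follows, and *and/or* is printed in the other four bullets. The larger counts (6, 4 and 10 of 24) depend on that reading, so the figures to rely on are 2 of 24 for re-haemorrhage and stroke and 0 of 24 for oedema. The combinations are unweighted and some are clinically unlikely.

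Finally, the >2 in the section 7.5.2.1 oedema bullet may come from the conversion of the document to text. It is raised only for confirmation.

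**Conclusion.** The concern holds, and it should be fixed. The direction of the GCS criterion is wrong in all six places, on the protocol's own use of both scales. Four of the six (re-haemorrhage and stroke in both sections) change under either reading of the text. Oedema in section 5.8.3 changes only if the comma adds a condition, and oedema in section 7.5.2.1 does not change because decompression already decides it. The practical effect therefore falls mainly on re-haemorrhage and stroke.

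The conclusion on direction needs no assumption about the comma or the oedema threshold. The counts assume that a qualifying lesion is present and describe logical combinations, not patients. The documents do not allow the number of patients to be computed. Thirty-day mortality, the mRS and technical endpoints, and the precision calculation are unaffected.

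**What to change.** - Replace *increase* with *decrease* for the GCS in all six places: three in section 5.8.3 and three in section 7.5.2.1. Leave the NIHSS wording as it is.
- Use one connector in both sections, so that it is clear whether decompression or death qualifies on its own. Correcting the direction does not settle this.
- Have the sponsor confirm the oedema GCS threshold against the source document and align the two sections if they do differ.
- Carry the agreed wording into the adverse event CRF, the study SOP and the DSMB charter wherever they repeat the definitions. Those documents are not shown, so whether they do is unknown.
- Re-check any re-haemorrhage, oedema or stroke event already classified, including lesions not counted under the printed wording.

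The cost is a wording amendment to two sections, matching edits to any dependent documents, and a review of recorded events. No new data collection is needed, and the endpoints and sample size do not change.
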